8 SUBJECT POPULATION

Approximately 120 subjects (approximately 8 to 20 subjects per site) are to be randomized at approximately 8 United States (US) sites to achieve approximately 110 subjects completed. An advertisement may be used to aid recruitment. The advertisement will be submitted to the IEC/IRB for approval. The IRB approved Pre-screening questionnaire will be provided before taking the consent.

The enrollment for the study is planned for 6 weeks. The expected duration of subject participation in the study (3 scheduled visits) is 30 ± 3 days per study period (up to 66 days total). The complete inclusion and exclusion criteria are presented in Section 8.1 and Section 8.2.

8.1 Inclusion Criteria

1. Age 45-65 (both inclusive) and must sign the informed consent.
2. Current adapted two-week/monthly replacement soft contact lens wearers (at least 2 months) with symptoms of contact lens induced dryness as defined by the Symptomatology (Eligibility) Pre-screening questionnaire.

Note: Subject may be wearing multifocal contact lenses or single vision contact lenses prescribed for monovision or for distance only.
3. Requires a near spectacle ADD of +0.50 or greater.
4. Best corrected visual acuity (BCVA) to 20/30 or better in each eye at distance at Visit 1.
5. Willing to wear lenses for a minimum of 5 days per week 6 hours per day, and attend all study visits.
6. Currently using a non-Alcon MPS to care for their lenses (at least 2 months).
7. Uses digital devices (eg, smart phone, tablet, laptop computer, or desktop computer) for 20 consecutive minutes at least twice a week and willing to continue the same pattern for the duration of the study as assessed at Pre-screening.

8.2 Exclusion Criteria

1. Extended wear (sleeps in lenses one or more nights per week).
2. Any anterior segment infection, inflammation, disease, or abnormality that contraindicates contact lens wear as determined by the Investigator.

3. Any use of systemic medications or ocular medications for which contact lens wear could be contraindicated, as determined by the Investigator, including use of any topical ocular medications that would require instillation during contact lens wear.
4. Monocular subjects (only 1 eye with functional vision) or subjects fit with only 1 lens.
5. A known sensitivity to any ingredients in OFPM.
6. Biomicroscopy findings observed during the Visit 1 slit-lamp examination that are moderate (grade 3) or worse in either eye.
7. Prior refractive surgery (eg, LASIK and PRK).
8. History of herpetic keratitis, ocular surgery, or irregular cornea.
9. A pathological dry eye that precludes contact lens wear.
10. Use of mechanical eyelid therapy or eyelid scrubs within 14 days before Visit 1 and not willing to discontinue during the study.
11. Enrollment of the Investigator or his/her staff, family members of the Investigator, family members of the Investigator's staff, or individuals living in the households of these individuals.
12. Enrollment of more than 1 member of the same household in the study.
13. Participation in any clinical study within 30 days of Visit 1.
14. Subjects who are currently using or have not discontinued RESTASIS, XIIDRA or a topical steroid within the past 7 days.

9 TREATMENTS ADMINISTERED

Upon completing the Pre-screening Questionnaire and satisfying the relevant pre-screening criteria, subjects will sign informed consent and then be considered enrolled into the study. A subject ID number will be assigned to enrolled subjects by entering the subject into the electronic data capture (EDC) system. Subjects eligible after Screening at Visit 1 will be randomized (1:1) to receive either OFPM or HMPS to care for their lenses in Period 1 of the study. For Period 2, the contact lens solution that was not allocated for use in Period 1 will be dispensed. Throughout the study, designated unmasked site personnel at the investigational site will be responsible for the accounting of all study products and will ensure that the study products are not used in any unauthorized manner.

9.1 Identity of Study Treatments

Investigational Product: OFPM

Control Product: HMPS

OFPM will be supplied in sterile 10 fl. oz. (300 mL) filled bottles with investigational labelling. A new lens case will be supplied with each bottle.

Table 9-1 Study Treatments

Properties	OFPM (Test product)	HMPS (Control product)
Administration	Subjects will use OFPM to store and disinfect their contact lenses as instructed by the study team member(s) dispensing the solution and according to the instructions for use.	Subjects will use their HMPS to store and disinfect their contact lenses as instructed by the study team member(s) dispensing the solution and according to the instructions for use.
Duration of Treatment	The subject will wear their habitual lens brand (following manufacturer recommended replacement) on a daily wear modality for 30 ± 3 days using OFPM daily to care for their lenses.	The subject will wear their habitual lens brand (following manufacturer recommended replacement) on a daily wear modality for 30 ± 3 days using their habitual solution daily to care for their lenses.
Quantity/Dosage	Up to 32 cleaning and disinfecting cycles will be used for the study.	Up to 32 cleaning and disinfection cycles will be used for the study.
Supply	OFPM will be supplied sterile, in 10 fl. oz. (300 mL) filled bottles	HMPS will either be: 1) Purchased by the subject and

Properties	OFPM (Test product)	HMPS (Control product)
	
with investigational labelling. A new lens case will be supplied with each bottle.
 
The study kit will contain one bottle of the test article (bottle will be re-labeled), and green and white screw top case. The product is manufactured by Alcon Laboratories in Fort Worth, Texas.
 
Note: Habitual rewetting drops may be used as needed throughout the study. Rewetting drop use frequency will be collected at baseline and follow-up.
	
reimbursed. The unmasked site personnel must confirm a new bottle of the HMPS identified at pre-screening is purchased by the subject and used for the assigned study period.
 
2) Purchased by the site according to the HMPS identified at pre-screening and dispensed to the subject for use during the assigned study period.
 
HMPS will be dispensed/used in commercial packaging. The manufacturer information for each product can be found in the package insert.
 
Note: Habitual rewetting drops may be used as needed throughout the study. Rewetting drop use frequency will be collected at baseline and follow-up.

OFPM will be provided in the commercial bottle but will be re-labeled. Included on the investigational labels for the randomized product will be the kit number, protocol number, fill volume, storage conditions, the indicator “Disinfecting Solution” and a statement that the product is for investigational use only. OFPM should be stored at room temperature.

More information on the OFPM or HMPS can be found in the Product Labeling. Refer to the MOP for product labels.

The new label will be sufficient to mask the OFPM, thus maintaining the subject masking to brand. A designated unmasked staff member at the site will be assigned to dispense the sealed test kit and the HMPS to ensure Investigator masking. Unmasked site personnel cannot conduct study specific procedures.

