1 SYNOPSIS

Sponsor: Alcon Research, Ltd.
[name]
[name]

Protocol Number: LCO115-P001

Investigational Product: Opti-Free PureMoist (OFPM)

Study Phase:

1 2

3 4

N/A

Protocol Title: Clinical Study of Opti-Free PureMoist for Presbyopic Contact Lens Wearers

Investigator(s)/ No. of Sites: Approximately 8 sites

Center Location(s)/ United States

No. of Subjects Duration of Treatment:

Required: 110 completed 30 ± 3 days per period each product (up to 66 days total)

[figure not shown]
Planned: approximately 120 randomized

(approximately 8 to 20 subjects per site)

Study Population: Current presbyopic soft contact lens wearers (2-week /monthly replacement modalities only) with symptoms of contact lens induced dryness and using a non-Alcon multi-purpose solution.

Objectives: The overall objective of this study is to demonstrate the benefit of OFPM compared to non-HYDRAGLYDE multipurpose contact lens solutions in presbyopes currently wearing soft contact lenses and experiencing symptoms of dryness.

[figure not shown]
[figure not shown]
The primary objective is to demonstrate superiority of OFPM when compared to the subject’s habitual multipurpose solution (HMPS) in reducing symptoms of contact lens induced dryness after 30 days of use, based on responses to the CLDEQ-8 (abbreviated Contact Lens Dry Eye Questionnaire).

Sponsor:

Alcon Research, Ltd.
[name]
[name]

Protocol Number: LCO115-P001

Methodology:

This is a prospective, randomized, crossover (2-treatment, 2-period), observer-masked, and quasi-subject-masked study.

Treatments:

Investigational Product: OFPM

Route of Administration: Thoroughly wet each side of the lens with OFPM solution. Rub the lens for 20 seconds. Rinse each side of the lens for 10 seconds with a steady stream of OFPM solution. Fill your Alcon lens case with fresh OFPM solution.

Refer to MOP for detailed instructions for use in the package insert.

Duration of Treatment: The subject will wear their habitual lens

Sponsor: Alcon Research, Ltd.
[name]
[name]

Protocol Number: LCO115-P001

brand (following manufacturer recommended replacement) on a daily wear basis for 30 ± 3 days using OFPM daily to care for their lenses.

Dosage: Up to 32 cleaning and disinfecting cycles will be used for the study.

Control Article: Habitual Multi-purpose Solution

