9.3 Accountability Procedures

Designated unmasked site personnel will dispense the study contact lens solutions (re-labeled OFPM and the site/subject purchased commercially labeled HMPS) in accordance with their assigned subject ID number and the randomization treatment order allocated to them. The identity of the test product will not be revealed to the subject and the order of use of the test and control products will not be revealed to the Investigator. It will not be possible to maintain full subject masking due to the nature of the cleansing devices, but the brand name will be masked for the test solution. During the study, the investigational site must maintain records of study treatment dispensation and collection by the unmasked personnel for each subject. This record must be made available to the designated study monitors for the purposes of verifying the accounting of clinical supplies. Any discrepancies and/or deficiencies between the observed disposition and the written account must be recorded along with a detailed explanation. Study contact lens cleaning devices associated with a device deficiency or with any product-related AEs must be returned to the Sponsor or manufacturer (for comparator/reference product). Refer to Section 12 for additional information on the reporting of device deficiencies or product-related AEs.

At the conclusion of the study, the Investigator will be responsible for returning all used and unused study supplies unless otherwise instructed by the Sponsor.

Upon receipt of the test products (OFPM test solution kits) from Alcon, the unmasked coordinator will conduct an inventory. During the study, the unmasked coordinator must maintain records of study treatment dispensation and collection for each subject including study solutions (test OFPM or purchased control HMPS). This record must be made available to the study monitor for the purposes of verifying the accounting of clinical supplies. Any discrepancies and/or deficiencies between the observed disposition and the written account must be recorded along with an explanation. At the conclusion of the study, the Investigator

will be responsible for returning all used and unused study supplies unless otherwise instructed by the Sponsor.

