9.4 Subject Confidentiality and Methods Used to Minimize Bias

The Investigator must ensure that the subject's anonymity is maintained throughout the course of the study. In particular, the Investigator must keep an enrollment log with confidential identifying information that corresponds to the subject numbers and initials of each study participant. At the end of the clinical study, the Sponsor will collect a copy of the enrollment log without any identifying subject information. All documents submitted to the Sponsor will identify the subjects exclusively by subject ID and demographic information. No other personally identifying information should be transmitted to the Sponsor.

The intent of masking is to limit the occurrence of conscious and unconscious bias in the conduct and interpretation of the clinical study. Bias could arise from the influence that the knowledge of a specific treatment assignment may have on the recruitment and allocation of subjects, their subsequent care, the assessment of end points, the handling of withdrawals, and so on. The essential aim of masking, therefore, is to prevent identification of the test article(s) by the Investigator, subject, and others associated with the conduct of the study until all such opportunities for bias have passed.

This study is Investigator-masked and subject quasi-masked (masked to test solution brand only), with subjects randomized to the order in which they will use OFPM and their HMPS for 30 ± 3 days each. The Investigator will not be aware of the specific treatment being administered and the subject will not be aware of the brand of the test solution. Alcon study personnel will be masked, with the exception of the following: Study monitor, Lead CSM, and person responsible for generating the randomization schedule. This level of masking will be maintained throughout the conduct of the study. Subjects will be assigned treatment order based on the randomization schedule; it will be blocked to ensure a balance of study treatment allocations within investigational sites. The randomization scheme will be generated and maintained by the Sponsor. In the event of a medical emergency where the knowledge of subject treatment is required, an individual Investigator will have the ability to unmask the treatment sequence assignment for a specific subject.

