10 STUDY PROCEDURES

10.1 Outline of Study

[figure not shown]
Prior to informed consent and scheduling the Screening visit, subjects will be given the Pre-screening Questionnaire (Symptomatology Questionnaire, Digital Device Use assessment and HMPS Identification Tool). These may be administered via a combination of phone, email, or in person; (Note: the HMPS Identification Tool is visual). Once the subject completes the questionnaire and the replies indicate the subject to be eligible to proceed then informed consent must be obtained from the subject before any procedure specified by this protocol is initiated, including Screening procedures at Visit 1. The original signed informed consent must be maintained with the subject's file whether they pass or fail Screening. A copy of the signed informed consent form will be provided to the subject. Data from the Pre-screening Questionnaire will not be entered into to the electronic case report forms (eCRFs) but will stay in the subject file as source documents for monitoring of both randomized subjects and screen failures. Those who pass pre-screening and sign informed consent may attend the Screening visit (Section 10.2.1).

Subjects who are scheduled to attend the Screening visit must have a new bottle of the HMPS identified during pre-screening ready for possible dispensing at the end of the Screening visit after randomization. This can be accomplished in two ways for the study:

- 1) The subject purchases a new bottle of the HMPS and brings it to the Screening visit. In this case the subject will be reimbursed for their purchase. The unmasked coordinator must confirm the solution purchased was the HMPS identified during pre-screening and that it is not expired. If HMPS is randomized to be used for Period 2, the site will maintain the purchased HMPS at the site for the subject until Period 2;
- 2) The site purchases the subject's HMPS and dispenses to the subject according to the randomization schedule.

Adverse events (AEs)/serious adverse events (SAEs) and device deficiencies will be assessed and reported at all scheduled and unscheduled study visits for each subject from the time of informed consent.

Figure 10-1 Diagram of Study Design

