11	Unmasked coordinator to assign/dispense the study lens care solution for Period 1 per randomization scheme. 1) HMPS purchased by the subject or provided by the site –or- 2) Investigational Masked OFPM Kit with Kit #. Educate on instructions for use.
12	Assess and record any adverse events (AEs) that are reported or observed from the time of informed consent (see Section 12).
13	Record any device deficiencies that are observed or reported.
14	Schedule Visit 2 (Period 1 Follow-up) to take place on Day 30 ± 3 days (scheduled 29 (± 3) days after Visit 1. Provide subject with Visit 2 reminder instructions: 
 The subject should bring the used lens case for the study period, along with their dispensed study lens care product used during the study period.

10.2.2 VISIT 2 – PERIOD 1/Day 30 & PERIOD 2/DAY 1

1	Document wear time compliance (days, hours) and lens care compliance. Collect used study lens care product from the subject.
2	Obtain information on any changes in medical health and/or the use of concomitant medications since Visit 1.
3	Have subject complete the Subjective Questionnaire based on lenses worn and study solution used during the 30 day study period (CLDEQ-8, [REDACTED] [REDACTED] [REDACTED])
4	Conduct Snellen VA with worn lenses. For details refer to MOP.
5	[REDACTED]

6	Remove lenses and perform biomicroscopy assessments using slit-lamp examination scales. For details and order of staining procedures, refer to MOP.
7	Perform subjective (manifest) refraction assessment and BCVA assessment (as needed). For details refer to MOP.
8	Assess and record AEs that are observed or reported (see Section 12).
9	Record any device deficiencies that are observed or reported.
10	Dispense a new pair of habitual lenses and perform Snellen VA with new lenses being dispensed at the visit. For details refer to MOP. For two-week replacement lens wearers, provide the subject an extra pair of study lenses for replacement at two weeks. Contact the subject at approximately 15 ± 1 days of the study period to remind the subject to replace their lenses and document date of replacement in the source.
11	Unmasked coordinator to assign/dispense the study lens care solution for Period 2 per randomization scheme. 1) HMPS purchased by the subject or provided by the site –or- 2) Investigational Masked OFPM Kit with Kit #. Educate on instructions for use.

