11.4.1 Primary Efficacy

The primary objective of this study is to demonstrate superiority of OFPM when compared to HMPS in reducing dryness symptomatology as measured by CLDEQ-8.

The corresponding endpoint is the score (range 0 to 37) from CLDEQ-8, obtained by adding the numerical responses to each of the 8 items, collected at the Day 30 follow-up for each product (Visit 2 and Visit 3).

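### Masking the test brand is the only subject-level protection for a self-reported primary score, and the protocol's claim that a bottle label is enough conflicts with its own kit and instruction text.

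*Protocol*

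**What the plan says.** **Endpoint and who reports it.** Protocol 11.4.1 and SAP 4.1 define the primary endpoint as "the score (range 0 to 37) from CLDEQ-8" at the Day 30 follow-up of each period. The subject fills it in. The Visit 2 procedure (Protocol 10.2.2) reads "Have subject complete the Subjective Questionnaire based on lenses worn and study solution used during the 30 day study period", and Visit 3 has a parallel step.

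**Level of masking.** Protocol 9.4 and SAP 1.4 describe the Investigator as masked and the subject as quasi-masked, that is, "masked to test solution brand only". Protocol 9.3 concedes that full subject masking cannot be achieved, but also says "The identity of the test product will not be revealed to the subject".

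**Presentation of the two products.** The habitual solution (HMPS) is used in its commercial packaging (Table 9-1). Under one of two supply options in 10.1, "The subject purchases a new bottle of the HMPS and brings it to the Screening visit". The test solution (OFPM) comes in its commercial bottle with a new label marked for investigational use. Table 9-1 adds: "The study kit will contain one bottle of the test article (bottle will be re-labeled), and green and white screw top case".

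**The sufficiency claim.** Section 9.1 concludes: "The new label will be sufficient to mask the OFPM, thus maintaining the subject masking to brand". The synopsis, under Route of Administration for the test product, gives the user instruction "Fill your Alcon lens case with fresh OFPM solution" and refers to the Manual of Procedures (MOP) for the package-insert instructions.

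**The concern.** Masking the Investigator does little for a score that the subject reports. What matters is what the subject knows. The subject knows which period uses the familiar solution, because it arrives in its own packaging and the other bottle is labelled investigational. The one thing still withheld is the brand of the new solution.

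The protocol rests that last safeguard on a bottle label. A label does not control what the bottle shape, the case or the written instructions reveal. Every subject enters as a user of a non-Alcon solution (inclusion criterion 6), so any cue to the sponsor's name would point to the test product.

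Subjects are enrolled because they have dryness symptoms on their current regimen, so a more favourable expectation of something new is plausible. If it exists, it goes wherever the product goes, and the analysis cannot separate it from a product effect. The superiority claim on which study success depends would then mix the two.

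**Working it through.** **1. The texts side by side**

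| Place | What it implies for brand masking |
|---|---|
| Protocol 9.1, closing text | The label alone is sufficient |
| Protocol 9.3 | The test identity is withheld from the subject |
| Protocol 9.1, label contents | No brand among the listed items |
| Protocol 9.1, bottle | Commercial bottle, so its shape is a possible cue |
| Table 9-1, test supply | Green and white case in the kit; no package insert listed; markings on the case not stated |
| Table 9-1, HMPS supply | No case mentioned |
| Synopsis, test product | Second-person instruction naming the manufacturer and the product abbreviation |
| Table 9-1 and 9.2 | Subject follows the instructions for use as given by the unmasked coordinator; no brand-neutral version specified |

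The sufficiency claim and the synopsis wording are compatible only if the subject never receives that wording or a branded case. The documents do not say.

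**2. Why the model does not help.** The primary model (Protocol 11.4.1.2, SAP 4.3.1) has terms for solution, period, sequence and baseline CLDEQ-8, with subject as a random effect. Let τ be the true product effect and b an expectation shift attached to the test product. Both enter whenever OFPM is in use and in no other period, so the estimated solution difference has expectation τ + b. Period and sequence are balanced against solution by design. Baseline is a single value per subject and cancels from the within-subject contrast. None of these terms separates b from τ.

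**3. Reproducing the plan's own figure.** Inputs from Protocol 11.10 and SAP 7: SD of paired differences 10, difference 3, one-sided α 0.05, power 80%.

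- Normal approximation: N = ((1.645 + 0.842) × 10 / 3)² = 68.7, rounded up to 69.
- Noncentral t with N − 2 df: smallest N = 71, rounded up to 72 for two equal sequences, i.e. 36 per sequence.
- Power at 72 is 80.9%. The stated 36 per sequence is reproduced.

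**4. How small a bias would matter.** Inputs: SD 10, and 110 completers (Protocol section 8). The size of b is **assumed**; the documents give none.

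- SE = 10 / √110 = 0.953.
- One-sided 5% threshold = 1.659 × 0.953 = 1.58 points.
- Relative to the design difference: 1.58 / 3 = 53%. Relative to the scale: 1.58 / 37 = 4.3%.

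Probability of declaring superiority with τ = 0 (noncentral t, N − 2 df, noncentrality b / SE):

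| Assumed b (points) | 110 completers, SD 10 | 110 completers, SD 6 to 12 | 72 completers, SD 10 |
|---|---|---|---|
| 0 | 5% | 5% | 5% |
| 0.5 | 13% | 22% to 11% | 11% |
| 1.0 | 27% | 54% to 22% | 21% |
| 1.5 | 47% | 83% to 37% | 35% |
| 2.0 | 67% | 97% to 54% | 51% |

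The SD range of 6 to 12 is also an assumption. With 72 completers the threshold is 1.96 points. The table shows what any product-linked bias of the given size would do, whatever its source.

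**The case against.** A reader might infer that the kit and instructions actually disclose the brand to subjects. The documents do not support that. The synopsis is written for sites and the sponsor, and OFPM is the protocol's own abbreviation. Section 9.2 has subjects follow instructions from the unmasked coordinator. The kit list contains no insert, the listed label items carry no brand, and nothing says that the case is marked. The MOP, which would settle the matter, is not among the documents. What stands is narrower: the texts conflict, and the label-only claim is asserted without support.

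A reader might also infer that expectation can push the score only towards OFPM. That is not shown either. Subjects have used their own solution for at least 2 months, an investigational-use label could cause wariness, and some novelty is shared because new lenses are dispensed in both periods and a new HMPS bottle is required. A shift towards the new product is plausible, but its direction is not established.

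The limitation is also partly declared. The plan calls itself quasi-masked, and comparison with the subject's own solution is its stated purpose, so some awareness is inherent. This is a fair point. It does not rescue the sufficiency claim, because 9.4 itself makes preventing identification of the test article, including by the subject, the aim of masking.

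Finally, the false-success figures do not measure brand leakage. Subjects would know which product is new even if the brand were perfectly hidden, and the same table would apply. This objection stands in full.

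**Conclusion.** The point holds in limited form. The primary score is self-reported, subjects can tell test from habitual, and brand masking is the only subject-level safeguard left. The protocol declares that safeguard secured by a label while its bottle, case and synopsis wording put it at risk, and these passages need reconciling. Whether the brand reaches subjects cannot be decided from the documents. No masking check or measure of expectation is visible, although some assessments are redacted.

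On size, the plan's own SD and completer target mean that about 1.58 points, roughly half the design difference, is enough for success. The figures of 27%, 47% and 67% for shifts of 1.0, 1.5 and 2.0 points are hypothetical. They rest on an assumed bias, zero true effect, SD 10 and 110 completers, and say nothing about how large an expectation effect is. This is an inexpensive improvement that the plan should make, not a demonstrated failure of the trial.

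**What to change.** - In Protocol 9.1 and Table 9-1, specify a lens case with no brand marking.
- In the same places, specify a subject instruction sheet that calls the product *Disinfecting Solution* (the term already on the investigational label), names neither the manufacturer nor OFPM, and keeps every warning and use step from the labeling.
- Align the Route of Administration wording in the synopsis with that sheet.
- Delete the statement that the label alone is sufficient. If neutral materials already exist in the MOP, say so in 9.1.
- State with the primary analysis (Protocol 11.4.1, SAP 4.3.1) that a superiority result may include an expectation effect, because subjects know which product is new.

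I would not go further by over-labelling or sleeving the HMPS bottle, or by withholding safety labeling. Subjects know their own solution, so little masking is gained, and Protocol 5.2 treats following the labeling as essential.

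The cost is plain cases for about 120 subjects, a reprinted sheet and a short text change. Masking would still be incomplete, because the bottle shape may be recognised.
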